6.2 Secondary Endpoints

This phase 1 study is not powered to detect statistically significant differences in efficacy.

However, data will be collected and described descriptively on the following endpoints:

- objective tumor response: objective response to therapy as determined by iRANO criteria (table 9)
- overall survival : time from study project injection to death
- progression-free survival : time from study project injection to first confirmed disease progression as determined by objective tumor response
- quality of life: summary score on patient self-report measure, Functional Assessment of Cancer Therapy- Brain component (as determined by patient self-report on FACT-Br v4, appendix C)

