10.3.2.3 Analysis of the Secondary Endpoint(S)

For objective tumor response, a summary table will be produced to present the number and proportion of responders in each arm, together with each of the response categories, namely CR, PR, MR, SD, P and PP.

The analysis of overall survival and progression-free survival are based on the survival function, estimated by the Kaplan-Meier method. Survival will be calculated from the day of study inclusion until progression and death, respectively, or will be censored at the date of last available follow-up information. The survival function will be summarized for 25th percentile, median, and 75th percentile, and the survival curves of the two arms will be presented.

Descriptive statistics will be used to describe the overall quality-of-life score on physical well-being, social/family well-being, emotional well-being, functional well-being and additional concerns, respectively.

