Appendix A. iRANO criteria	
Term	Criteria
Complete Response (CR)	The enhancing tumor is no longer seen by neuroimaging, with the patient off all steroids, or on adrenal maintenance only.
Partial Response (PR)	Decrease of $\geq 50\%$ in the product of two diameters with the patient on a stable or decreasing dose of steroids, with a stable or improving neurologic examination for at least six weeks.
Minor Response (MR)	Decrease in diameter products of $< 50\%$ with the patient on a stable or decreasing dose of steroids, with a stable or improving neurologic examination for at least six weeks.
Stable Disease (SD)	The scan shows no change. Patients should be receiving stable or decreasing doses of steroids.
Progression (P)	Increase of $> 25\%$ in tumor area (two diameters) provided that the patient has not had his/her dose of steroids decreased since the last evaluation period. A concomitant decrease in steroid dose will rule out a progression designation during the first two months after completion of radiation
Pseudoprogression (PP)	Radiological changes without concomitant neurological changes. It is not unusual to see enhancement in the context of oncolytic viral therapies. If thought to be the case, serial MRI imaging is warranted.

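### The Appendix A response categories leave gaps and overlap, and Progression has no explicit term for new lesions or clinical decline, so PFS can miss clinical failure and Minor Response is not evidence of activity

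*Combined protocol and SAP*

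**What the plan says.** Appendix A lists six categories.

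- **Minor Response (MR):** "Decrease in diameter products of" less than 50%, "with the patient on a stable or decreasing dose of steroids, with a stable or improving neurologic examination for at least six weeks". There is no minimum decrease. Partial Response (PR) carries the same conditions with a decrease of at least 50%.
- **Stable Disease (SD):** "The scan shows no change. Patients should be receiving stable or decreasing doses of steroids". No band is given, and no neurological condition.
- **Progression (P):** an increase above 25% "in tumor area (two diameters) provided that the patient has not had his/her dose of steroids decreased since the last evaluation period". The row names no reference scan, new lesion or clinical deterioration.
- **Pseudoprogression (PP):** "Radiological changes without concomitant neurological changes", with no size, direction or rule for later conversion to P.
- **Complete Response (CR):** enhancing tumor gone, off steroids or on adrenal maintenance only.

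Section 6.2 defines PFS as "time from study project injection to first confirmed disease progression as determined by objective tumor response". Section 10.3.2.3 follows PFS to progression and OS to death, and otherwise censors at last follow-up. Neither section names death or clinical deterioration as a PFS event. Section 10.3.2.3 also tabulates "the number and proportion of responders in each arm, together with each of the response categories" without saying which categories make a responder.

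**The concern.** A response scale should give every assessment exactly one category. Here a trivial shrinkage can be an MR, and SD requires an identical diameter product. An increase of up to 25% is neither SD nor P. A patient who worsens neurologically while the scan changes little cannot reach P.

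Two outputs depend on this. PFS takes its event from P alone, so an incomplete P delays or removes events. The response table has a row labelled as a response that measurement error can fill. Progression also ends the eight-weekly visits in Section 4.9 and the quality-of-life and first-year MRI schedule in Table 4, so the definition affects which data are collected.

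**Working it through.** The plan states no sample size, event count or power for response or PFS, so there is no figure to reproduce. Two checks apply.

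**1. Coverage of the categories.** I crossed six size bands (gone; down 50-99%; down 1-49%; no change; up 1-25%; up more than 25%) with four steroid states (off, decreasing, stable, increasing) and two examination states (stable or improved; worse): 6 × 4 × 2 = 48 cells. Being off steroids counts as meeting the stable-or-decreasing condition. The six-week requirement is taken as met when the examination is stable or improved. PP is first ignored, then read literally as any size change without neurological worsening.

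| Size band (8 cells each) | No category, PP ignored | No category, PP literal | More than one, PP literal |
|---|---|---|---|
| Gone | 4 | 3 | 3 |
| Down 50-99% | 5 | 4 | 3 |
| Down 1-49% | 5 | 4 | 3 |
| No change | 2 | 2 | 0 |
| Up 1-25% | 8 | 4 | 0 |
| Up more than 25% | 2 | 1 | 3 |
| Total of 48 | 26 | 18 | 12 |

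- Up 1-25%: the four cells with a stable or improved examination become PP. The four with a worse examination have no category.
- Overlaps: PP coincides with CR, PR, MR and P. An increase above 25% without neurological change is both P and PP, unless steroids were reduced.
- Clinical decline without an increase above 25%: 5 size bands × 4 steroid states = 20 cells. None is P. Sixteen have no category, three are SD (unchanged scan, steroids not rising) and one is CR.
- Unchanged scan with rising steroids: no category, whatever the examination.

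**2. Measurement error.** Assumed, not from the documents: no true change, two diameters of 20 or 40 mm, each read with independent error of 3%, 5% or 10% and rounded to 1 mm. Let r = (follow-up product ÷ baseline product) − 1. The MR size rule is −0.5 < r < 0.

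| Error, diameter | MR size rule | r = 0 | 0 < r ≤ 0.25 | r > 0.25 | Decrease on two scans, same baseline |
|---|---|---|---|---|---|
| 3%, 20 mm | 38% | 24% | 38% | 0% | 22% |
| 3%, 40 mm | 46% | 9% | 46% | 0% | 29% |
| 5%, 20 mm | 44% | 12% | 43% | 1% | 28% |
| 5%, 40 mm | 48% | 4% | 47% | 2% | 32% |
| 10%, 20 mm | 48% | 4% | 35% | 13% | 32% |
| 10%, 40 mm | 50% | 1% | 36% | 13% | 33% |

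The r > 0.25 column is the false-P rate at one scan. Against a common reference at 10% error, at least one false P occurs in about 28% of patients over three scans and 39% over six. If two consecutive scans must agree, these fall to about 7-8% and 13-14%. At 5% error the single-call figures are about 3-4% and 6%.

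**The case against.** The case for leaving the table alone has real content.

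- A reader might infer that any decrease scores MR. It does not: steroids must be stable or decreasing and the examination stable or improving for at least six weeks.
- A reader might infer that an increase of up to 25% never has a category. Read literally, PP covers it when there is no neurological change.
- A reader might infer that a new lesion can never produce P. There is no explicit criterion, but P is judged on tumor area, and Appendix A does not say whether a new lesion's area is included.
- A reader might infer that response and PFS are both biased upward. Uncategorised results are indeterminate rather than favourable, false P calls shorten PFS, and the responder proportion rises only if MR is counted, which Section 10.3.2.3 does not say.
- A reader might convert the 38-50% into a count, such as half of an 18-patient arm. That needs full enrolment and a measurable lesion in every patient, yet Arm B may be injected into a tumor bed after resection. All patients also receive radiation and temozolomide, so no true change is an artificial reference case.

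The analysis is descriptive, each category is tabulated and by-subject listings are promised, so CR plus PR could be recovered. Section 10.3 promises a fuller SAP before database lock. Section 6.2 also refers to a Table 9 for the criteria. It does not appear in the available text, so whether Appendix A is the complete rule set cannot be confirmed.

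These points limit the size and direction of the claim. They do not supply a band for SD, a floor for MR, a clinical term for P or a precedence rule for PP. Listings cannot recover a progression date that the stated rule never generates.

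**Conclusion.** The concern holds in a limited form. The stated categories are neither exhaustive nor exclusive, and this is a fault in a written rule rather than missing detail. The firmest consequence is for PFS: clinical failure without an area increase above 25% is missed or censored, which by itself lengthens PFS. Because false P calls work against this, the documents do not support a net figure or direction.

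For response, the MR row cannot be read as activity. Under the assumed error range, 38-50% of single scans with measurable disease meet its size rule by chance, or 22-33% if a decrease is required on two scans against the same baseline. These rates apply to patients who also meet the steroid and neurological conditions. They rest on assumed error, not on trial data. The primary endpoint is untouched.

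**What to change.** Amend Appendix A and Sections 6.2 and 10.3.2.3, and carry the wording into the SAP before database lock:

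1. Define SD as every change between the MR or PR limit and the P limit. Give MR a prespecified lower limit beyond measurement error, or merge smaller decreases into SD.
2. For the PFS endpoint, add to P any new lesion and clear clinical deterioration not explained by other causes. State how a new lesion enters tumor area and how the confirmation requirement in Section 6.2 applies.
3. Assign a category to an unchanged scan with rising steroids. State when PP takes precedence over, or converts to, another category, so that each assessment has exactly one. Reconcile the two steroid sentences in the P row: one has no time limit, the other covers only the first two months after radiation.
4. In Section 10.3.2.3, define responders as CR plus PR, with MR listed but not counted.

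The cost is amendment wording. No extra scans or visits are needed, since neurological examination and KPS are already in Table 5. The downside is a lower reported response proportion, possibly shorter PFS, and a judgement on the cause of clinical decline that must be documented in an open-label trial.
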